We will be administering a medication to patients – prednisone – which is not a new drug and is not investigational. It is an accepted treatment of patients with subacute thyroiditis at similar doses to what we are proposing. The regimen recommended by the ATA guidelines for treatment of subacute thyroiditis is: Prednisone 40mg x 1-2 weeks followed by gradual taper of 2-4 weeks⁹. We propose that the anti-inflammatory effects of this medication that we know are effective in non-surgical thyroiditis patients will be beneficial in the immediate pre-operative period.

Physical Risks

Prednisone is a common medication prescribed often for inflammatory conditions. A recent review found that 1 in 5 adults in this country over 3 years received at least 1 prescription for short term use of corticosteroids for various conditions such as allergies, respiratory tract infections¹⁵. Long term use is associated with severe risks such as fungal, viral or opportunistic infections, poorly controlled blood glucose, avascular necrosis, fracture, hypertension, weight gain, poor wound healing, venous thromboembolism, and risks to a fetus in pregnancy. Risks of a short course are generally low, as the risks are dose and duration dependent. Risks of a short course (1 week) of prednisone include elevated blood sugar, increased risk of infection, venous thromboembolism, and bone fractures. The absolute risks in one well done study showed that the 90-day risk of a hospitalization for sepsis after a <30 day course of corticosteroids was 0.05% compared to 0.02% for non-users. Risk of venous thromboembolism was 0.14% compared to 0.09% of non-users, and risk of fracture was 0.51% compared with 0.39% of non-users. Additionally, there may be side effects of taking the medication such as nausea, gastrointestinal upset, appetite changes, mood changes, or insomnia. The risk of wound infection for thyroid surgery is low – less than 0.5%, and we will exclude pregnant patients, patients with diabetes who are at higher risk of elevated blood glucose, and patients with other immunocompromised states.

Specific Aims/Study Objectives:

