 - Confidentiality will be protected further by: (1) using a participant log form that contains only the minimum necessary protected health information (PHI) concerning participants, and storing this log in a locked area when not in use, (2) not sharing PHI with any outside institution, (3) coding data collection forms with a consecutive participant number that is not derived from any participant personal identifiers, and linking that data collection form to the participant log, and (4) storing the participant log, the key linking the code to the PHI, and data collection forms separately.
 - It is highly likely that these measures will result in avoidance of breach of confidentiality outside of the research. In addition, the data to be collected are not sensitive to participants.
- **Study Procedures:**
 - Eligible patients will have a diagnosis of autoimmune thyroiditis, positive auto-antibodies, and an indication or preference for surgical treatment with a total thyroidectomy. This will be a randomized, non-blinded pilot study, and all patients who are eligible will be given the opportunity to participate.
 - Preoperative Testing: All randomized patients will undergo our current standard of care pre-operative testing, which includes a clinic ultrasound and laboratory testing of thyroid function and autoantibody levels. All study patients will be directed to complete the online quality of life surveys (SF-12 and ThyPRO) prior to surgery. Each survey will take approximately 10-20 minutes to complete. Patients randomized to the steroid arm will be given a prescription for prednisone 20 mg daily for 7 days prior to surgery. Patients will be instructed to take the prednisone once a day, in the morning, with food. All patients (steroid or not) will receive our standard instructions for TUMS and saturated iodine (in Graves' disease) if indicated. Our current standard of care for patients with Graves' disease is to take 1-2 drops of saturated iodine solution

twice a day and 1000mg of TUMS three times a day for the 7 days leading up to surgery. There is no consistent regimen for TUMS or saturated iodine for patients with Hashimoto's in our clinic, but it is up to the clinical judgement of the surgeon whether to use these medications on an individual basis. There are no interactions of these medications with prednisone, and administration or non-use of these medications does not exclude anyone from participating in the trial.

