- 2 weeks postoperatively: Patients are all seen in clinic 10-14 days after surgery and calcium and PTH hormone levels are checked as per our standard of care. Research specific labs of antibody levels will be checked for our study patients (15-45 mL, depending on individual antibody profiles of subjects).
- 6 weeks postoperatively: Patients are all given a lab slip to have thyroid stimulating hormone (TSH) and thyroxine (FT4) drawn to check levothyroxine dosing as per our standard of care, as well as checking antibodies to monitor for treatment success. This can be done at a lab of their choosing. Patients will be sent an electronic link to fill out the quality of life surveys (SF-12 and ThyPRO).

- **6 months postoperatively:** Patients have TSH and FT4 drawn again to check levothyroxine dosing as per our standard of care, as well as checking antibodies to monitor for treatment success. Again, this can be drawn at the lab of their choice. Patients will be sent an electronic link to fill out the quality of life surveys (SF-12 and ThyPRO).

Time point	Procedures (all standard of care)	Labs (italics are current standard of care, black are study specific and in the budget)	Surveys (study specific)
Preop clinic visit (2-4 weeks preop)	Ultrasound with color doppler quantification of blood flow, vocal fold ultrasound	Ca, PTH, TSH, FT4, Tg, TgAb, TSI, TPO, TRAB	SF-12, ThyPRO
Day of Surgery	Repeat ultrasound with color doppler	TgAb/TPO/TSI/ TRAB for any that were positive preop	Thyroid difficulty scale (surgeon)
2 weeks postop	Clinical voice assessment, vocal fold ultrasound	Ca, PTH, TgAb/TSI/TPO/TRAB if they were positive	
6 weeks postop	Laryngoscopy if clinically indicated	TSH, FT4, Tg, TgAb/TSI/TPO/TRAB if they were positive	SF-12, ThyPRO
6 months postop		TSH, FT4, TgAb/TSI/TPO/TRAB if they were positive	SF-12, ThyPRO

- **Study Drug:**
 - Rx will be provided to patients randomized to steroid prep group for “Prednisone 20mg tabs. Sig: Seven days before your scheduled surgery, Take 1 tab (20mg) daily in the morning for 7 daysTake with food. Disp: 7 tabs. Refills: none”
 - Patients will fill this at the UW American Center outpatient pharmacy at no charge, no drug accountability procedures are required for this commercially available drug that is being used in the standard of care dosing and route.

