 - Concomitant medications allowed/disallowed: No other steroids or immunosuppressive medications, No antibiotics, antitubercular drugs, or anti-fungals. No anticoagulants. Caution in many anti-seizure medications.
 - No placebo
 - While chronic systemic steroids may impair wound healing, there is literature to support that acute (< 10 days), high-dose systemic corticosteroid use has no clinically significant effect on wound healing¹⁴
 - The prednisone dose is within the accepted guidelines for rapid prep for Graves’ disease patients, and is considered a moderate dose. It is expected to contribute negligible increased risk for wound complications in this population where wound infection rates are already extremely low (less than 0.5%).
- **Data and Safety Monitoring Plan:**
 - This is a study that involves randomizing patients to receive a prescription drug, therefore is greater than a minimal risk study. It is using a commonly prescribed medication for a short duration and has been shown to have a low incidence of adverse events at these doses and durations. Prednisone is already prescribed

in a subset of similar patients to our population outside the context of a trial (Graves' disease requiring rapid surgical prep). Potential problems will be monitored and handled by the primary surgeon, clinic staff and principal investigator. This is appropriate given the small number of participants (15 subjects will receive the intervention drug), single site, and low risk medication. We will not assemble a formal *external* Data and Safety monitoring committee..

- [name] will be notified by the enrolling surgeon each time a subject enrolls in the trial and of any protocol deviations. Adverse events from the study medication will be reported immediately. We anticipate that the manner in which subjects will report adverse events is by (1) directly notifying the principal investigator as directed in the informed consent document, (2) calling our clinic staff who will notify [name], or (3) by reporting side effects and amount of drug taken on the drug compliance survey on the day of surgery.
- Protocol violations and deviations, side effects, and adverse events will be noted in the secure RedCap database.
- A monthly clinical research meeting occurs among our group to discuss all clinical research, and this study will become a standing item on our agenda during the duration of the trial for any surgeon to discuss possible adverse events or concerns

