- Given low rates of wound infection in this population, any wound infection requiring treatment with antibiotics in the steroid group will be considered an adverse event (AE) and will be investigated immediately by the principal investigator and operating surgeon, and reported to the IRB within 14 business days. If a wound infection requires an operation, it is considered a serious adverse event (SAE), although it is not immediately life threatening or debilitating to other subjects, so also will be reported with 14 business days to the IRB. If a second wound infection requiring antibiotics or surgery occurs in the steroid treated group, enrollment will immediately cease and it will be reported as a SAE in the same 14 day timeframe, when we will closely scrutinize these cases with the help of the IRB to determine whether it is safe to proceed. Monitoring for wound infections will occur in the context of our usual clinical care. We will see every wound in person at the postoperative visit, but otherwise we rely on patients self-reporting to alert clinic staff if they have concerns (redness, warmth, drainage) about their incisions. No specific study-specific instructions will be given to study subjects, we will simply ask them to call the clinic staff if they have any concerns, and clinic staff will be trained to immediately notify [name] if a study patient reports wound complications.
- Statistical Considerations: Provides an explanation as to why the number of subjects was chosen and the means for analyzing data will meet the specific aims/study objectives
 - As a small pilot, feasibility study, the size of 30 is based on our estimate of a realistic recruitment rate for the future definitive trial. We see approximately 70 potential subjects in our clinics per year, and our listed exclusion criteria are rare in our population. We estimate that fewer than one fourth will not meet criteria, and an additional one fourth may decline to participate. From the patient perspective, enrollment involves only answering QoL surveys and possibly taking a medication 1 week prior to surgery, the risks and effort are not much greater, which is why we estimate a generous rate of inclusion. We are giving ourselves 1 year to enroll all 30 patients (with an additional 6 months to collect follow up data). Our biostatistics team has already been engaged and feels this is an aggressive but realistic expectation. For all primary aims, data will be analyzed

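### No question or examination for steroid harm is scheduled after the 10-14 day visit, so later events, including most of the 90 days over which sepsis risk is quoted, depend on unprompted patient reports

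*Combined protocol and SAP*

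**What the plan says.** Under Physical Risks, the protocol lists infection, venous thromboembolism and fracture among the risks of a one-week course. For sepsis it reports that "the 90-day risk of a hospitalization for sepsis after a <30 day course of corticosteroids was 0.05% compared to 0.02% for non-users". It continues: "Risk of venous thromboembolism was 0.14% compared to 0.09% of non-users, and risk of fracture was 0.51% compared with 0.39% of non-users". The 90-day period is written for sepsis only and is not restated for the other two.

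The Data and Safety Monitoring Plan gives three routes by which adverse events are expected to surface: the patient tells the principal investigator, as the consent document directs; the patient calls clinic staff, who pass it on; or the event emerges "by reporting side effects and amount of drug taken on the drug compliance survey on the day of surgery". Only the third is a scheduled question.

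On wounds, the same section says "We will see every wound in person at the postoperative visit, but otherwise we rely on patients self-reporting to alert clinic staff". It adds "No specific study-specific instructions will be given to study subjects", but that sentence goes on to say that patients will be asked to call if they have concerns and that staff will be trained to alert the investigator at once. A second infection treated with antibiotics or surgery in the steroid group halts enrolment pending review with the IRB.

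Under Study Procedures, "Patients are all seen in clinic 10-14 days after surgery". The time-point table lists voice assessment, vocal fold ultrasound and laboratory tests for that visit. At 6 weeks and again at 6 months there are blood tests at a laboratory of the patient's choice, and "Patients will be sent an electronic link to fill out the quality of life surveys (SF-12 and ThyPRO)". The only later procedure is laryngoscopy at 6 weeks, if clinically indicated.

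**The concern.** The first specific aim covers the safety as well as the benefit of prednisone, and the pilot is meant to inform a larger trial. Yet after about two postoperative weeks nobody is scheduled to ask about, or look for, the harms that the protocol itself names. A wound infection treated by another practice in week four, or an admission elsewhere for sepsis or a clot, enters the data only if the patient thinks to report it. The list of items to be extracted from medical records (Research Design and Methods) names no admission, infection, thromboembolism or fracture, so no planned chart search backs up self-report. No end date for collecting adverse events is given either.

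Two things are at stake. First, a statement that no harms occurred could not be read as more than that none was volunteered. Second, the rule that halts enrolment works on a count of wound infections, and an incomplete count makes it less sensitive. The trial is also unblinded, and the plan defines wound infection as an adverse event only for the steroid group, so voluntary reporting may not be comparable between the arms.

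**Working it through.** The plan has no calculation of its own to reproduce here: the risks are quoted from a cited study and the sample size of 30 rests on feasibility.

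**1. Share of the 90 days after the last visit.** Inputs: "prednisone 20 mg daily for 7 days prior to surgery" (first dose on about day -7, last on about day -1) and the visit on postoperative day 10-14 (both Study Procedures); 90 days (Physical Risks, sepsis). Share remaining = (90 - days elapsed at the visit) / 90.

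| Clock starts at | Days elapsed at visit | Days remaining | Share |
|---|---|---|---|
| First dose | 17-21 | 69-73 | 77-81% |
| Last dose | 11-15 | 75-79 | 83-88% |
| Surgery | 10-14 | 76-80 | 84-89% |

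Most of the period follows the visit on any of these clocks.

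**2. Expected events at the quoted rates.** Inputs: 15 patients per arm (Study population) and the three pairs of rates. This assumes that the rates apply to these patients.

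- Steroid arm: 15 × (0.05% + 0.14% + 0.51%) = 15 × 0.70% = 0.105 events. Chance of at least one: 1 - (1 - 0.007)^15 = 10.0%.
- Control arm: 15 × (0.02% + 0.09% + 0.39%) = 15 × 0.50% = 0.075 events. Chance of at least one: 7.2%.
- If all three risks ran evenly over 90 days from first dose (an assumption), steroid-arm events after the visit would number 0.105 × 69/90 to 0.105 × 73/90 = 0.081 to 0.085.
- Even with complete capture, 0 of 15 has a one-sided 95% upper limit of 1 - 0.05^(1/15) = 18%.

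**3. Sensitivity of the wound-infection rule.** With X ~ Binomial(15, p × c), where p is the true infection rate and c the fraction that becomes known, P(X ≥ 2) = 1 - (1 - pc)^15 - 15pc(1 - pc)^14. The protocol gives a background rate below 0.5%. The higher rates and all values of c below 1 are assumptions.

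| True rate p | c = 1 | c = 0.7 | c = 0.5 |
|---|---|---|---|
| 0.5% | 0.25% | 0.12% | 0.06% |
| 5% | 17% | 9.5% | 5.3% |
| 10% | 45% | 28% | 17% |

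At the protocol's own rate the rule almost never fires, whatever the capture. Under-reporting costs appreciable sensitivity only if steroids raise infection well above that rate.

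**4. What the 6-week contact could add.** Day 42 after surgery is day 49 from first dose, leaving 41 of 90 days (46%). A 6-month question, looking back, spans the whole period.

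**The case against.** The best defence is that reporting is passive but not absent. Patients are asked to call, the consent document directs them to notify the investigator, staff are trained to escalate, events go into the study database, and safety is a standing item at a monthly meeting. The consent form is not in the published text, so what patients are told, and for how long, cannot be judged. The protocol also calls feasibility the pilot's real primary aim, and Statistical Considerations says that patients are followed closely for six weeks or more.

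Much of this stands, and it rules out several stronger readings:

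- A reader might infer that safety coverage stops about three weeks after the first dose. It does not: the call-in route has no closing date. Later coverage is less sensitive, not missing.
- A reader might take all three serious risks as 90-day figures. The text attaches that period to sepsis alone.
- A reader might apply the 77-81% to wound infections or to the enrolment rule. The documents give no 90-day figure for wound infection, and every wound is inspected at 10-14 days.
- A reader might infer that one unreported infection disables the rule. That is so only when exactly two occur, which is 59% of triggering cases at an assumed 10% rate and 28% at 20%.

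The defence does not supply a scheduled question. The six-week statement names no check for harm, the meeting can discuss only what is already known, and a small, low-risk study argues against extra visits rather than against a few extra questions.

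**Conclusion.** The concern holds as a modest weakness in how harms are ascertained. After the 10-14 day visit the plan neither asks about nor looks for steroid harm, while 69-73 of the 90 days used for the sepsis figure, counted from first dose, are still to come. Later events will therefore be captured less completely than earlier ones, by an amount that the documents do not allow us to estimate.

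The numerical consequence for this pilot is small. About 0.1 events of the three named kinds are expected in the steroid arm, and the trial could not estimate those risks even with perfect capture. The drop from 45% to 28% in the chance of reaching two wound infections rests on an assumed 10% infection rate, at least 20 times the stated background, and an assumed 70% capture applied to all infections, including those visible at the clinic visit. It shows what would be lost if steroids did serious harm; it is not a forecast. The change is worth making because safety is in the first aim, the definitive trial will draw on these data, and the remedy uses contacts already planned.

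**What to change.** Add a short adverse-event block, identical in both arms, to the electronic links already sent at 6 weeks and 6 months. Ask, with dates, about any wound infection treated with antibiotics anywhere, any hospital admission or emergency visit, any blood clot and any fracture. State the date on which adverse-event collection ends for each patient. Send positive answers to the principal investigator for confirmation in the chart, so that confirmed wound infections in the steroid group count under the existing rule.

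Rely mainly on the 6-week answers for timely detection. The 6-month answers would span the full 90 days, but Statistical Considerations expects those data to be harder to obtain, recall will be weaker, and replies may arrive too late to affect a one-year enrolment. Both remain self-report, though prompted.

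The cost is a few database questions, about two minutes per patient, some reported events to confirm and an IRB amendment. No visit or staff post is added.
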